Inclusion Criteria: a. willing and able to give written or virtual informed consent; b. men or women, 25-55 years of age or at PI's discretion; c. a primary diagnosis of DSM-V MD or Bipolar II current episode, depressed, as diagnosed by the SCID- Structured Clinical Interview for DSM-V Axis I Disorders (SCID-V) V; d. score of >10 on the PHQ-9 and a score of 2 or greater on item #1 of the PHQ-9; e. off all antidepressant or other psychotropic therapy (e.g. mood stabilizers, antipsychotics, and sedative hypnotics) for at least 4 weeks prior to baseline visit (8 weeks for fluoxetine) Concomitant administration of up to 2 mg of clonazepam or its equivalent per day will be allowed, but not within 12 hours of study assessments f. CRP>2mg/L, and g. IDS-SR anhedonia subscale (Items 8,19,21) score ≥5. Exclusion Criteria: a. current autoimmune disorder; b. history of hepatitis B or C infection or human immunodeficiency virus infection: c. history of any type of cancer requiring treatment with more than minor surgery; d. unstable cardiovascular, endocrinologic, hematologic, hepatic, renal, or neurologic disease (as determined by physical examination and laboratory testing); e. history of any (non-mood-related) psychotic disorder; active psychotic symptoms of any type; history of Bipolar I Disorder; substance abuse/dependence within 6 months of study entry (as determined by SCID) or any 2 year period of continued substance abuse; f. an active eating disorder or antisocial personality disorder; g. a history of a cognitive disorder unless otherwise approved by the PI; h. pregnancy or lactation; i. chronic use of nonsteroidal anti-inflammatory agents (NSAIDS) (excluding 81mg of aspirin), glucocorticoid containing medications; j. use of NSAIDS or oral glucocorticoids at any time during the study; k. any contraindication for MRI scanning; I. failure of more than 2 antidepressant trials in the current episode; m. Intolerance of bupropion or escitalopram and n. BMI >40 (to exclude severe obesity). Due to the high co-morbidity between anxiety disorders and depression, we plan to include patients with anxiety-related disorders excluding OCD if depression is the primary diagnosis. Patients with stable medical conditions and on medications for those conditions will not be excluded. Concomitant administration of up to 2 mg of clonazepam or its equivalent per day will be allowed, but not within 12 hours of study assessments. m. sexually active participants will be asked not to become pregnant during study participation. Pregnancy tests will be conducted at screening, baseline, and treatment weeks 4 and 8.

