
Description of Study Procedures

Appointment Scheduling & Reminders: All participants will be given the opportunity to receive appointment reminders and scheduling information via text message on their mobile phones. If the subject consents to this form of communication, study staff may use OhMD Texting Service to communicate with participants. This platform provides a Desktop and Mobile Version of OhMD for the research team to securely communicate with participants and maintain subject confidentiality. This service will only be used for communicating relevant appointment information and never used for PHI. Participants will receive the following text message from the study team upon first contact: "Please do NOT send any personal information via text. You may call the study team at [contact] to discuss any personal or health details." Any PHI received via text message will be reported to the IRB as a potential breach of confidentiality.

Screening: Screening will include: (1) Past psychiatric history and current symptom severity by clinical interview and using a modified Structured Clinical Interview for DSM-V (SCID-V), 38 and the PHQ-9 39 (2) Psychiatric treatment history in current episode using the MGH Antidepressant Treatment Response Questionnaire (ATRQ), 40 (3) Medical history from patient interview and review of medical records, (4) Complete medical and neurological examination (5) Screening laboratory evaluation, (6) Vital signs, height and weight and (7) hsCRP (obtained twice over a 2-week period at the P.I's discretion as per AHA/CDC guidelines to establish stability, and along with physical examination and laboratory testing to rule out acute inflammation or infection (which may influence DA neurotransmission). The PI may request to perform a rapid CRP test at screening using the Diazyme hsCRP POC Test Kit. This kit produces rapid results using a finger prick method to collect 20µl of blood and is intended for the in vitro quantitative determination of C-reactive protein. Screening laboratory evaluations may be repeated at PI's or PI designee's discretion. Additional assessments will be conducted if more than 4 weeks from screening, unless otherwise approved by the PI, study physician or PI's designee.

PI: [name] Sponsor: NIMH

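### Seizures are named as a bupropion risk, but no criterion excludes a controlled or past seizure disorder, and the stable-conditions sentence points towards admitting treated patients

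*Combined protocol and SAP*

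**What the plan says.** Section 12 (Potential Study Risks) includes seizures in its list of bupropion side effects; its list for escitalopram does not. Section 13, under bupropion or escitalopram treatment, names seizures again among the risks of the study drugs.

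Eligibility is set out in section 5, Participant Selection. The parts that bear on a patient with a seizure disorder are:

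- Exclusion d: "unstable cardiovascular, endocrinologic, hematologic, hepatic, renal, or neurologic disease (as determined by physical examination and laboratory testing".
- Exclusion k: "any contraindication for MRI scanning".
- Exclusion m: "Intolerance of bupropion or escitalopram".
- Inclusion e, which requires patients to be "off all antidepressant or other psychotropic therapy (e.g. mood stabilizers, antipsychotics, and sedative hypnotics" for at least four weeks before baseline. Clonazepam, or an equivalent, is allowed up to 2 mg per day.
- The closing sentence on comorbidity: "Patients with stable medical conditions and on medications for those conditions will not be excluded".

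Screening, also in section 5, includes "Medical history from patient interview and review of medical records, (4) Complete medical and neurological examination". Section 6 adds collateral history. Investigational Drug Status, in section 13, says the drugs will follow their package inserts for dose and duration; it does not extend this to patient selection.

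**The concern.** The protocol names a serious hazard of one study drug but has no entry rule for the patients in whom that hazard is the most obvious worry. Two groups are left open:

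1. **Controlled and treated.** Patients with a stable seizure disorder whose medication does not count as a psychotropic under inclusion e. For them the text is not merely silent: the stable-conditions sentence says they stay in.
2. **Past seizure, no medication.** The stable-conditions sentence does not cover them, and neither does any exclusion item.

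What is at stake is patient safety. Patients and study staff are blinded, so those adjusting the dose do not know which drug it is. Under Baseline and Study Procedures, anyone with a HAM-D-17 score above 7 at two weeks moves to the higher dose as tolerated, which in the bupropion arm is 300 mg/d. A Table 1 footnote allows the increase at week 2 or week 4. Screening is therefore the main point at which a known susceptibility can be acted on.

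**Working it through.** The plan has no figure to reproduce. The check sets the eligibility text against the two groups and then looks for any later text that closes the gap.

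**Exclusion items, section 5**

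- Lettered items a to n: 14. The list ends with a second item lettered m, about pregnancy, which is not counted.
- Items naming seizure or epilepsy: 0 of 14.
- Items excluding on history: b (hepatitis or HIV), c ("history of any type of cancer requiring treatment with more than minor surgery"), e (psychotic disorder, Bipolar I) and g ("a history of a cognitive disorder unless otherwise approved by the PI"), so 4 of 14.
- Item d, the only one naming neurologic disease, is not worded by history.

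**Each possible barrier against each group**

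| Text | Group 1: controlled, treated | Group 2: past seizure, untreated |
|---|---|---|
| Exclusion d | Not reached: the disease is stable | Not reached: no unstable disease is present |
| Exclusion k | MRI contraindications only | MRI contraindications only |
| Exclusion m | Intolerance of a study drug only | Intolerance of a study drug only |
| Inclusion e | Bars those whose drug counts as a psychotropic, such as a mood stabilizer; does not bar the rest | Does not apply |
| Stable-conditions sentence | Says not excluded | Does not apply |

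Item d would remove an uncontrolled seizure disorder. It assesses disease by physical examination and laboratory testing, whereas a controlled or past seizure disorder is mainly a matter of history. The laboratory panel in the Table 1 footnote (metabolic panel, TSH, blood count, CRP) does not assess seizure history.

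**Later text**

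- The discontinuation rules in section 5 and in section 13 (the treatment subsection and Stopping Rules) cover suicidality, psychotic or catatonic symptoms, worsening on the HAM-D-17, missed doses and pregnancy. Some versions add mania or hypomania. The treatment subsection also lists hospitalization and imminent threat to self or others, but only between screening and baseline. None names seizure.
- The package-insert statement covers dose and duration only.

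**Exposure of a patient who gets through**

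The planned number randomised is 50. Allocation of 1:1 is inferred from 20 analysed per group (section 11) and blocks of 4 (section 5). The chance of bupropion is then 25/50 = 1/2, for up to 8 weeks and up to 300 mg/d.

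**The case against.** The strongest reply is that the documents never say a seizure history raises the risk on bupropion; they only list seizures as a side effect. Hypertension is in the same list, and both drugs are said to be able to induce mania. Yet stable hypertension is not excluded and Bipolar II is expressly admitted, so the protocol does not pair each side effect with a history exclusion. Part of this stands: the documents give no size for any added risk, and the argument cannot rest on a general pairing rule. But the protocol gives the other two hazards some follow-up. Vital signs are scheduled through the study, and mania appears in some discontinuation lists. Seizure has no entry rule and no discontinuation rule. It needs no outside figure to be cautious about giving a seizure-prone patient a drug that the protocol says can cause seizures.

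A second reply is that screening gathers medical history, records, a neurological examination and collateral information, so a clinician would probably decline such a patient. That is fair: the stable-conditions sentence does not oblige anyone to randomise a particular patient. It remains true that no written criterion tells staff to act on the history, and for treated patients the wording points the other way.

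Third, existing safeguards narrow the gap: unstable neurologic disease, recent substance abuse or dependence, active eating disorder and current psychotropic drugs are all barred, apart from the clonazepam allowance. This limits how many patients are affected but closes neither group. The mixed wording of the exclusion items also does not prove an oversight; it shows only that the authors excluded on history where they chose to.

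**Conclusion.** The concern holds as a low-cost patient-safety improvement. By its text, the plan does not exclude a past seizure or a controlled seizure disorder treated with a drug outside the washout, and for the treated group it leans towards admission. The group with a past seizure and no medication rests on silence alone, which is the weaker half of the point.

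The size cannot be put as a number of patients or events. The documents give no prevalence and no harm rate; in a trial of 50 the number affected may be small or zero. What can be said is that none of the 14 exclusion items names seizure and that, if allocation is 1:1, any such patient randomised has a 1 in 2 chance of bupropion. The point has no bearing on the estimand, power or analysis.

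**What to change.** Add a separate exclusion item to section 5 for seizure disorder or history of seizure, in the same history-based form as items b, c, e and g, to be judged on medical history as well as examination. The study's medical team should settle the exact wording, including how to treat remote or provoked events, since the documents do not say how far each raises the risk. Add a clause stating that the stable-conditions sentence does not override this item.

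The cost is one line of protocol text and one entry on the screening checklist. The information is already collected at screening, so no new procedure is needed. The downside is perhaps a few more screen failures, in a trial whose interim-analysis note already reports slow recruitment.

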Criteria for Study Discontinuation ("Stopping Rules"):

Individual:

To reduce the risks associated with active treatment, all subjects will be monitored carefully for the development of adverse events as well as worsening of their condition. Between signing consent and completing the screening assessment, a period of no more than 2 weeks will pass until baseline. Subjects will be closely evaluated throughout the study both virtually and during study visits for worsening of psychiatric symptoms. Moreover, all patients are provided 24/7 access to study personnel in the event of an emergency. Subjects will be discontinued at any point for any of the following: 1) the development of significant suicidal ideation, plan or intent as determined by spontaneous subject report or as determined by CSSRS,⁴¹ 2) the development of psychotic or catatonic symptoms, 3) a 25% increase from baseline of HAM-D-17 score, 4) missing more than 2 consecutive doses of medication more than once during the study, and 5) positive pregnancy test. Subjects requiring discontinuation will be referred for further evaluation and treatment by one of the study psychiatrists.

1) If more than two individuals experience a reportable serious adverse event related to study procedures within a six-month period, the study will be stopped and reviewed by the DSMB.

Neuropsychiatric Assessments

Structured Clinical Interview for DSM-V Axis I Disorders (SCID-V) is a semi-structured clinical interview that provides a wide range of DSM-V diagnoses. ⁴² All patients will be evaluated by a modified SCID as part of the screening process. In addition to providing information for inclusion/exclusion purposes, the SCID will provide data about psychiatric predictors of treatment response, including number of past major depressive episodes, length of the current episode and presence of co-morbid anxiety disorders and/or dysthymia.

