12. Potential Study Risks: There are 5 major areas of potential risk in the proposed study stemming from 1) neuropsychiatric assessments, 2) blood drawing, 3) fMRI scanning, 4) medication administration, and 5) loss of confidentiality. Neuropsychiatric assessments may uncover strong and potentially

PI: [name] Sponsor: NIMH

disturbing feelings about the subject's past or present emotional state. The risks of blood drawing include discomfort, bruising, infection, bleeding, and fainting. Undergoing fMRI scanning poses no more risk than undergoing a routine MRI scan. Physical discomfort due to lying in the scanner, occasional headaches due to scanner sounds and previously unrecognized claustrophobic attacks are the prominent adverse effects of the procedure. Use of bupropion has been associated with several side effects including anorexia, dry mouth, rash, sweating, tinnitus, tremors, hypertension and seizures. Use of escitalopram has been associated with appetite changes, headache, sweating, indigestion, nausea, tremors and sexual dysfunction. Both drugs can induce mania and suicidal ideation. Finally, there is a risk of loss of confidentiality. Confidentiality of all subjects will be protected per institutional and NIH and other federal requirements, and as described in greater detail below.

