Risks and side effects of these medications vary in type and severity depending on the drug, but include gastrointestinal distress, headaches, sexual dysfunction, anxiety, high blood pressure, induction of mania, suicidal ideation, seizures and potential lethality in overdose. To reduce the risks associated with active treatment, all subjects will be monitored carefully for the development of adverse events as well as worsening of their condition. Specific indications for discontinuation between screening and baseline will include any of the following at the Pl's discretion: 1) the development of significant suicidal ideation, plan or intent as determined by spontaneous subject report or as determined by CSSRS, 41 2) the development of psychotic, manic/hypomanic or catatonic symptoms, 3) a 25% increase from baseline of HAM-D-17-17 score. 4) missing more than 2 consecutive doses of medication more than once during the study, and 5) a positive pregnancy test at any point during the study. Other criteria for discontinuation between screening and the baseline visit include: hospitalization for any reason or a clinical judgment that a subject is an imminent threat to self or others. Upon discontinuation, subjects will be immediately evaluated by a study psychiatrist and determination of the appropriate level of care, including emergency hospitalization, will be determined. Subjects with non-urgent symptoms but who disqualify for further participation and who are in active treatment will be referred to their primary psychiatric physician. Participants will be required to identify a primary care or psychiatric physician at study entry to ensure seamless psychiatric care following study completion. All depressed subjects without a current psychiatrist will be offered an appropriate referral. The unblinded study physician may break the treatment blind following study completion or early termination from study participation. Participants with adequate treatment response at study completion may receive a 4 week supply of identified study medication. At the end of the study, or in the event of Early Termination, patients not achieving a 50% or greater treatment response as measured by the Ham-D-17 total score, they will be given a prescription to continue medication for 1 tablet daily for 7 days before stopping the medication (if on 2 pills of study medication at the end of the study). An individualized plan will be crafted for each subject to ensure psychiatric back-up should emergency psychiatric care be required after hours or on weekends. During the treatment study itself, subjects will be discontinued at any point for any of the following: 1) the development of significant suicidal ideation, plan or intent as determined by spontaneous subject report or as determined by the Columbia Suicide Severity Rating Scale, 2) the development of psychotic or catatonic symptoms, 3) a 25% increase from baseline of HAM-D-17 score, 4) missing more than 2 consecutive doses of medication more than once during the study and 5) positive pregnancy test at any point during the study. Subjects requiring discontinuation will be referred for further evaluation and treatment by one of the study psychiatrists as described above.

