Subjects will be closely evaluated throughout the study for worsening of psychiatric symptoms. Subjects will be discontinued at any point for any of the following at the Pl's discretion: 1) the development of significant suicidal ideation, plan or intent as determined by spontaneous subject report or as determined by CSSRS,⁴¹ 2) the development of psychotic, manic/hypomanic or catatonic symptoms, 3) a 25% increase from baseline of HAM-D-17 score, 4) missing more than 2 doses of medication more than once during the study, and 5 a positive pregnancy test at any time during the study. Subjects requiring discontinuation will be referred for further evaluation and treatment by one of the study psychiatrists or clinicians.

Compensation to Participants:

Participants will receive up to \$400-\$1500 for participation of the study. Participants will be compensated using ClinCard. The ClinCard is a web based, reloadable, debit card that automates reimbursements for clinical research participants. An additional \$25 will be provided to cover travel expenses for participants that travel equal to or greater than 50 miles to Atlanta. Candidates deemed ineligible by virtual evaluation(s)prior to the first in person office visit will not be compensated.

Visit	Total Amount	Amount put on Clincard immediately after visit	Amount put on Clincard at the end of study participation
Intake (Virtual when possible)	No Payment	No Payment	No Payment
(Visit Total)			
Visit 1 (Screen A)			
Screening lab work, UDS, Preg Test, AEs, Concomitant Meds	\$50*	\$50*	
(Visit Total)	\$50		
Visit 2 (Screen B & Baseline A)			
Physical Exam, Rapid CRP, Vitals, research bloods, urine toxicology and pregnancy test, self-report surveys	\$50	\$50	
Computer Task (depending on choice made on the computer)	\$5-\$10	\$5-\$10	
(Visit Total)	\$55-\$60		
Visit 3 (Baseline B)			
Medical and psychiatric assessments, vitals, self-report surveys and medication check and randomization and medication administration	\$50	\$50	
Computer Task (depending on choice made on the computer)	\$5-\$30	\$5-\$30	
Complete Scan	\$200		\$200
Incomplete Scan	\$25**	\$25**	
(Visit Total)	\$80-\$280		
Visit 4 (Week 2)			
Medical and psychiatric assessments, self-report surveys and medication check	\$50	\$50	

PI: [name] Sponsor: NIMH

Sponsor: NIMH			
Computer Task (depending on choice	\$5-\$10	\$5-\$10	
made on the computer) (Visit Total)	\$55-\$60		
Visit 5 (Week 4)			
Medical and psychiatric assessments,	\$50	\$50	

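### The individual discontinuation rules for the treatment period are inconsistent: two lists are mandatory and silent on mania, while a third is discretionary, adds mania/hypomania and words the missed-dose rule differently.

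*Combined protocol and SAP*

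**What the plan says.** Four lists of individual discontinuation criteria stand in the current text.

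- **Section 5, Criteria for Study Discontinuation.** The instruction carries no discretion clause: "Subjects will be discontinued at any point for any of the following: 1) the development of significant suicidal ideation". The psychiatric criterion reads "2) the development of psychotic or catatonic symptoms", and a 25% rise in HAM-D-17 over baseline follows it. The missed-dose criterion is more than 2 consecutive doses, more than once.
- **Section 13, paragraph on bupropion or escitalopram treatment, treatment-phase list.** This is introduced as applying during the treatment study itself. It is mandatory and uses the same criteria as Section 5.
- **Section 13, Stopping Rules.** This also applies at any point, but at the principal investigator's discretion. The psychiatric criterion is "the development of psychotic, manic/hypomanic or catatonic symptoms", and the adherence criterion is "missing more than 2 doses of medication more than once during the study".
- **Section 13, paragraph on bupropion or escitalopram treatment, earlier list.** This is introduced as "Specific indications for discontinuation between screening and baseline". It is discretionary, names manic/hypomanic symptoms and keeps the word *consecutive*.

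Two other statements bear on the point. The inclusion criteria in Section 5 admit patients with "a primary diagnosis of DSM-V MD or Bipolar II current episode, depressed". Section 12 says "Both drugs can induce mania and suicidal ideation".

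**The concern.** A site following the protocol could reach different decisions about the same patient, depending on which section is open. For a patient with significant suicidal ideation or a 25% rise in HAM-D-17, the difference is between an obligation to stop and a judgement call. For a patient who becomes hypomanic without psychosis, it is whether a listed criterion exists at all. The plan makes that case foreseeable by enrolling Bipolar II patients, requiring mood stabilisers to have been stopped at least 4 weeks before baseline, and naming mania as a risk of both drugs.

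There is a statistical side as well. The primary endpoint in Section 10 is connectivity at 8 weeks, and the interim analysis, which can end the study, is triggered when 16 subjects have completed. These rules help decide who completes, so an ambiguous rule leaves part of the attrition mechanism undefined.

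**Working it through.** No sample size, power or alpha figure depends on this point, so there is nothing to recompute. The check is a comparison of the lists, criterion by criterion.

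| Criterion | Section 5 | Section 13, treatment phase | Section 13, Stopping Rules | Section 13, screening to baseline |
|---|---|---|---|---|
| Force | Mandatory | Mandatory | Investigator's discretion | Investigator's discretion |
| Psychotic or catatonic symptoms | Yes | Yes | Yes | Yes |
| Manic/hypomanic symptoms | Not named | Not named | Named | Named |
| Missed doses, more than once | More than 2 consecutive | More than 2 consecutive | More than 2 | More than 2 consecutive |
| Suicidality, 25% HAM-D-17 rise, pregnancy | Yes | Yes | Yes | Yes |

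**Count over the three lists that apply during treatment.** Mandatory in 2, discretionary in 1. Mania/hypomania not named in 2, named in 1. *Consecutive* present in 2, absent in 1. In each case the odd one out is the Stopping Rules paragraph. Nothing in the documents says which list prevails.

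**Cases in which the lists diverge.**

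1. Significant suicidal ideation, or a 25% HAM-D-17 rise, on treatment: discontinuation is required under two lists and discretionary under the third. The criteria are essentially the same but their force is not.
2. Hypomania without psychosis on treatment: not a listed criterion in two lists, a discretionary one in the third.
3. Two separate episodes, each with three non-adjacent missed doses: the two lists that say *consecutive* are not met, while the Stopping Rules wording can be.

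**Scope of the fourth list.** Table 1 places randomisation at Baseline B, so no study drug is dispensed before then. A list confined to screening through baseline should have no occasion to refer to missed study doses or to a HAM-D-17 rise from baseline, yet this one does. Either its heading or its contents are out of place. If it was meant to apply study-wide, the counts become 2 against 2 on mania, 2 against 2 on force, and 3 against 1 on *consecutive*. The inconsistency survives either reading.

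**Who is exposed.** Section 5 randomises 50 to obtain 40 with complete data, so 50 − 40 = 10 are projected to leave, and 10/50 = 20%. The rules therefore apply to all 50 for as long as each is treated, which will not be 8 weeks for everyone. Section 11 gives 36 as the total needed for the primary comparison, so the plan's own margin is 40 − 36 = 4 completers. How many patients would be classified differently under the competing lists cannot be derived: the documents give no expected number of Bipolar II patients and no rates for mania, missed doses or worsening.

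**The case against.** The best defence is to read the lists cumulatively. The two shorter lists are silent on mania; they do not say that a manic patient continues. The Stopping Rules paragraph applies at any point and names manic/hypomanic symptoms, so the protocol as a whole does contain an on-treatment mania criterion. That stands. A reader might infer from the side-by-side comparison that the plan has no such trigger, or that the lists flatly contradict each other on mania, and the text supports neither. What remains is that the only on-treatment trigger is discretionary, and that two mandatory lists omit a condition the protocol elsewhere names separately from psychosis.

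On missed doses, three of the four lists say *consecutive*, and the version without it is hard to apply, because it gives no window for deciding when a second episode has occurred. A dropped word is a plausible explanation. It needs correcting but would not carry the point alone.

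There are also safeguards. Bipolar I is excluded, a Bipolarity index is taken at intake, adverse events and CGI are recorded through treatment, worsening of psychiatric symptoms is monitored, and patients have round-the-clock access to study personnel. Emergent mania is therefore not unmonitored, although Table 1 shows no mania rating scale. Monitoring does not settle what is to be done with what it finds.

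Finally, patients and staff are blinded, which limits differential bias between arms. It does not make the rule uniform across patients.

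None of this answers the conflict between mandatory and discretionary.

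**Conclusion.** The point holds as an internal inconsistency in a safety rule: the plan is wrong as written, and this is not a matter of design preference. In order of weight, the conflicts are:

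1. Mandatory against discretionary, which extends to the suicidality and HAM-D-17 criteria.
2. Mania/hypomania, absent from two on-treatment lists and only discretionary in the third.
3. The missing *consecutive*.

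The unclear scope of the screening-to-baseline list adds to the need for reconciliation.

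A reader might go further and infer that the conflict will distort attrition or cost power. The documents do not support a figure for either. The effect on who reaches the week-8 scan is possible but unquantified, and no stated power calculation changes. On the statistical ground alone this would be a modest wording correction. It must be fixed because of patient safety, given Bipolar II eligibility and the stated risk of mania. The conclusion assumes only that all four lists are current text and that no precedence rule exists outside these documents.

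**What to change.** Reconcile the Section 5 list, both lists in the Section 13 treatment paragraph, and the Section 13 Stopping Rules paragraph into one consistent set of individual discontinuation rules. State which period each list covers, and replace the duplicates with cross-references.

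The clinical team needs to settle, and the text needs to state once:

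- whether each criterion is mandatory or discretionary;
- how manic/hypomanic symptoms are handled during treatment;
- which missed-dose definition applies;
- what the screening-to-baseline list is meant to govern.

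This review takes no position on those answers.

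The cost is a protocol wording amendment, with no additional patients, visits or procedures.
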